Generally, an AD reaction will quickly diminish once the initiating stimulus that caused the reaction is removed. To reduce the risk of an AD response, all participants will be encouraged to completely empty their bladder prior to each muscle conditioning or rowing session. The risk of an AD response should also decrease as training progresses and a participant's muscles become conditioned from the electrical stimulation. Thus, the risk of AD is highest during the initial muscle conditioning session. During a participant's first muscle conditioning session we will assess the ability of their muscles to respond to the electrical stimulation and we will pay particular attention to any signs of an AD response. It is possible that an AD response that is greater than mild might be identified at a participant's initial session and that could mean that they are not an acceptable candidate for continuation in the study.

It should also be noted that an individual's likelihood of having an AD episode in response to exercising part of the body below the level of a spinal cord injury will be heightened if an individual already has an underlying condition that is perceived by their body as a noxious stimulus. For example, an individual with a bladder infection might be more prone to an AD episode from an additional stimulus, such as Functional Electrical Stimulation of the legs, compared to an individual without a bladder infection. Therefore, it is important that any underlying noxious stimulus that might predispose an individual to an AD response is identified as early as possible and addressed before commencing or continuing with the rowing exercise.

We should note that FES-rowing research groups in England and Boston have never had a participant in their FES-rowing programs experience a severe case of AD, and those participants who have experienced

Title : Skeletal Health in the Lower Limbs Following Spinal Cord Injury
Approval Period: 01/13/2015 - 09/02/2015

mild cases of AD also experience mild cases during their everyday lives. Therefore, we believe the risk of experiencing a severe case of AD from participation in this study is very low, although the possibility of experiencing a mild case of AD is higher. At the first sign of an AD response, electrical stimulation will be stopped. Additional medical treatment in the case of a severe AD response will be available in our testing facilities.

5) Lower limb fracture during muscle conditioning, strength testing or FES-assisted rowing: The use of FES to stimulate paralyzed muscles in individuals with SCI has been studied for more than 50 years. Over that 50-year period there have been two reported cases of a fracture related to the use of functional electrical stimulation. One individual fractured their patella and a second individual fractured their lateral femoral condyle. Although the total number of individuals with SCI who have used functional electrical stimulation to exercise the lower limbs is not known, we believe the risk of a fracture is very low given that there have only been two reported fractures in 50 years of FES use. To further reduce the risk of fracture, only participants who have never experienced a low-energy or fragility fracture will be allowed to take part in this study. In addition, we will measure bone density for each participant at the beginning of the study and those measurements will provide us with an initial assessment of the health of each participant's femur and tibia. If we believe a participant's bones are too weak to safely undergo the muscle conditioning and rowing exercise, that participant will be withdrawn from the study.

6) Increase in neuropathic pain to an unacceptable level: Some spinal cord injured individuals suffer from neuropathic pain which can range from a mild tickling sensation to a severe burning sensation. It is not known what effect, if any, electrical stimulation has on this condition. In addition, some individuals with SCI who have some sensation in their thighs may find the electrical stimulation to be uncomfortable or even intolerable. Any participant who finds the electrical stimulation to produce neuropathic pain or sensation that is unacceptable to them will be withdrawn from the study.

7) Increase in spasticity to an unmanageable level: It is not known what effect FES has on the intensity and frequency of spasticity. In other FES-rowing programs, a few participants have had an increase in spasticity, while some participants have had a decrease. In general, spasticity levels should be reduced after a muscle conditioning or rowing session, since the muscles will be fatigued. If a subject experiences increased spasticity to a level that is unmanageable, they will be withdrawn from the study.

The risks of the Radioisotopes/radiation-producing machines (e.g., X-rays, CT scans, fluoroscopy) and associated risks.

Both of the bone density scanners we will use involve very low exposures to X-ray radiation. The total radiation exposure from all four visits will be 19.2 microSv. For comparison, a person can be expected to receive 8 microSv of natural background radiation per day from the environment. For an additional comparison, a person can be expected to receive approximately 30 microSv of radiation during an airline flight from San Francisco to New York. Therefore, the total additional radiation from the bone density scans is equivalent to slightly more than 2 days of natural background radiation and slightly more than half the radiation from a coast-to-coast airline flight. There are no known hazards from radiation at such a low level. This radiation dose is considered safe to administer to humans except during pregnancy. Although there are no documented risks to a fetus, we will exclude any subject who might be pregnant at the time of the study.

The risks of the Physical well-being.

None other than those described above.

The risks of the Psychological well-being.

We do not anticipate that any research-related procedure will adversely affect the psychological well-being of the participants.

The risks of the Economic well-being.

We do not anticipate that any research-related procedure will adversely affect the economic well-being of the participants.

The risks of the Social well-being.

We do not anticipate that any research-related procedure will adversely affect the social well-being of the

Title : Skeletal Health in the Lower Limbs Following Spinal Cord Injury
Approval Period: 01/13/2015 - 09/02/2015

participants.

Overall evaluation of Risk.

Low - innocuous procedures such as phlebotomy, urine or stool collection, no therapeutic agent, or safe therapeutic agent such as the use of an FDA approved drug or device.

- b) If you are conducting international research, describe the qualifications/preparations that enable you to both estimate and minimize risks to participants. Also complete the International Research Form and attach it in the Attachments section. If not applicable, enter N/A.**

N/A

- c) Describe the planned procedures for protecting against and minimizing all potential risks. Include the means for monitoring to detect hazards to the participant (and/or to a potential fetus if applicable). Include steps to minimize risks to the confidentiality of identifiable information.**

Confidentiality of the identifiable information will be carefully protected and data security measures will be strictly enforced. Any information or data on paper, including signed consents, will be stored in locked cabinets in locked offices in a secure VA building. All electronic data that contain identifiable subject information will be saved on a secure VA file server behind the VA firewall. No data will be maintained on portable electronic devices.

Protecting against and minimizing potential risks: To reiterate, the following are the potential risks to participants in the FES-rowing group.

- 1) Soft tissue reaction during FES training
- 2) Muscle strain during muscle conditioning, strength testing or FES-assisted rowing
- 3) Fall during transfer to or from rowing machine
- 4) Serious autonomic dysreflexia (AD) during FES training
- 5) Lower limb fracture during muscle conditioning, strength testing or FES-assisted rowing
- 6) Increase in neuropathic pain to an unacceptable level
- 7) Increase in spasticity to an unmanageable level

The following paragraphs describe how these risks will be mitigated to reduce them to the lowest possible levels.

1) Soft tissue reaction: Other than the typical reddening beneath the electrodes, which is to be expected, we will be vigilant to look for other types of soft tissue reactions and we will encourage all participants to be vigilant. To the best of our knowledge no prior FES-rowing participants have experienced a skin breakdown or pressure sore caused by their participation in an FES-rowing program. Nevertheless, before and after each session, we will look for any signs of bruising or swelling that might be suggestive of tissue breakdown, paying particular attention to the shoulders, back, buttocks, upper calves and knee areas.

2) Muscle strain: We will inform all participants of the possibility of a muscle strain and encourage participants that it is not necessary to perform at levels which push personal boundaries of performance, especially in terms of the energy which they exert when pulling on the handle of the rowing machine with their arms, since excessive upper body exertion is the more likely cause of muscle strain in the torso. Since subjects with SCI can have normal arm strength it is possible that a subject might believe that intensive arm pulling is required or encouraged. We will make it clear to participants that intensive arm pulling is not required. We will also discuss with each participant the experience of other FES-rowing groups so that our rowers are aware of the possibility of a muscle strain and let them know that they should tell us immediately if they think they have experienced a muscle strain. Since this risk has actually been observed in two

Title : Skeletal Health in the Lower Limbs Following Spinal Cord Injury
Approval Period: 01/13/2015 - 09/02/2015

FES-rowers in another research group, the possibility of a muscle strain is more than a theoretical possibility and we want to minimize that possibility by adequately informing our participants.

3) Risk of a fall during transfers: The risk of falling during transfers can be minimized to a very low level by using safe transfer techniques. [name], who has worked with patients with SCI for more than 30 years, is knowledgeable in what constitutes safe transfer techniques. [name] will observe each participant when they are first required to perform transfer in the study and based upon his observations he will recommendation for improving their transfer technique if needed.

4) Serious autonomic dysreflexia (AD) during FES training: To reduce the risk of an AD response, all participants will be encouraged to completely empty their bladder prior to each muscle conditioning or rowing session. We will also inform participants that the risk of an AD response is increased if they have an underlying condition which their body perceives as a noxious stimulus, such as a bladder infection. We will ask each participant to inform us if they have a known or suspected bladder infection. We will also inform participants that it may be necessary for them to take a break from their training or rowing while a bladder infection is treated.

The risk of an AD response should also decrease as training progresses and a participant's muscles become conditioned from the electrical stimulation. Thus, the risk of AD will be highest during the initial muscle conditioning session. During the initial muscle conditioning session for each participant, we will pay particular attention to any signs of an AD response. At the first sign of an AD response, electrical stimulation will be stopped. Additional medical treatment (e.g., the application of Nitropaste) in the case of a severe AD response will be available in our research facilities. Given that no other FES-rowing group has ever reported a severe AD response we believe the likelihood of a participant having a severe AD response is very low, however, all of our research staff and each participant will be informed about the possibility of AD response and we will be vigilant in looking for an AD response.

5) Lower limb fracture during muscle conditioning, strength testing or FES-assisted rowing: To reduce the risk of fracture, only participants who have never experienced a low-energy or fragility fracture will be allowed to take part in this study. In addition, we will measure bone density for each participant at the beginning of the study and those measurements will provide us with an initial assessment of the health of each participant's femur and tibia. If we believe a participant's bones are too weak to safely undergo the muscle conditioning and rowing exercise, we will not allow that participant to continue in the study. In addition, participants will be educated on potential signs of a fracture for a person with SCI who is insensate in the area; these include localized redness and swelling, excess spasticity, possibly excess sweating and/or AD. We believe this is unlikely, but the added precaution of educating the participant will allow him/her to be extra vigilant for this occurrence.

6) Increase in neuropathic pain to an unacceptable level: Some spinal cord injured individuals suffer from neuropathic pain which can range from a mild tickling sensation to a severe burning sensation. It is not known what effect, if any, electrical stimulation has on this condition. In addition, some individuals with SCI who have some sensation in their thighs may find the electrical stimulation to be uncomfortable or even intolerable. Any participant who finds the electrical stimulation to produce neuropathic pain or sensation that is unacceptable to them will be withdrawn from the study.

7) Increase in spasticity to an unmanageable level: It is not known what effect FES has on the intensity and frequency of spasticity. In other FES-rowing programs, a few participants have had an increase in spasticity, while some participants have had a decrease. In general, spasticity levels should be reduced after a muscle conditioning or rowing session, since the muscles will be fatigued. If a subject experiences increased spasticity that is unmanageable, they will be withdrawn from the study.

- d) **Explain the point at which the experiment will terminate. If appropriate, include the standards for the termination of the participation of the individual participant Also discuss plans for ensuring necessary medical or professional intervention in the event of adverse effects to the participants.**

Given the low risk level and given the success of other FES-rowing research studies, we do not anticipate

Title : Skeletal Health in the Lower Limbs Following Spinal Cord Injury
Approval Period: 01/13/2015 - 09/02/2015

terminating the study before the two-year funding period ends.

However, individual participants may be withdrawn from the study for several reasons, including, but not limited to:

- Inadequate muscle response to electrical stimulation
- Severe AD reaction in response to exercise or electrical stimulation
- Markedly low bone density compared to other individuals with acute and sub-acute SCI
- An increase in neuropathic pain or pain sensation from electrical stimulation to an unacceptable level
- An increase in spasticity to an unmanageable level

e) **Data Safety and Monitoring Plan (DSMP).** See guidance on **Data Safety and Monitoring.**

A Data and Safety Monitoring Plan (DSMP) is required for studies that present Medium or High risk to participants. (See Overall Evaluation of Risk above). If Low Risk, a DSMP may not be necessary. Multi-site Phase III clinical trials funded by NIH require the DSM Plan to have a Data Safety Monitoring Board or Committee (DSMC or DSMB). The FDA recommends that all multi-site clinical trials that involve interventions that have potential for greater than minimal risk to study participants also have a DSMB or DSMC.

The role of the DSMC or DSMB is to ensure the safety of participants by analyzing pooled data from all sites, and to oversee the validity and integrity of the data. Depending on the degree of risk and the complexity of the protocol, monitoring may be performed by an independent committee, a board (DSMC/DSMB), a sponsor's Data Safety Committee (DSC), a Medical Monitor, a sponsor's safety officer, or by the Protocol Director (PD).

Describe the following:

What type of data and/or events will be reviewed under the monitoring plan, e.g. adverse events, protocol deviations, aggregate data?

We will look for and track any adverse events, including unanticipated problems, that may occur during FES muscle-conditioning or FES rowing sessions. We will also be vigilant for any security breaches involving paper or electronic records.

Identify who will be responsible for Data and Safety Monitoring for this study, e.g. Stanford Cancer Institute DSMC, an independent monitoring committee, the sponsor, Stanford investigators independent of the study, the PD, or other person(s).

The PI/PD, [name] and Co-PD & Co-Investigator, [name], will be responsible for monitoring the data collected, including data related to unanticipated problems and adverse events.

Provide the scope and composition of the monitoring board, committee, or safety monitor, e.g., information about each member's relevant experience or area of expertise. If the Monitor is the Stanford Cancer Center DSMC or the PD, enter N/A.

PD and co-PD have extensive experience with regards to monitoring and maintaining safety of events/data related to this study.

Confirm that you will report Serious Adverse Events (SAEs), Suspected Unexpected Serious Adverse Reactions (SUSARs), or Unanticipated Problems (UPs) to the person or committee monitoring the study in accordance with Sponsor requirements and FDA regulations.

Serious Adverse Events (SAEs) and/or Unanticipated Problems (UAPs) are considered unlikely . Given the nature of this study, with each participant closely supervised and monitored regularly during muscle

Title : Skeletal Health in the Lower Limbs Following Spinal Cord Injury
Approval Period: 01/13/2015 - 09/02/2015

conditioning and rowing sessions, there should be minimal delay in reporting if any AE/UAP occur.

If applicable, how frequently will the Monitoring Committee meet? Will the Monitoring Committee provide written recommendations about continuing the study to the Sponsor and IRB?

As needed. As above, these are not considered likely to occur at all nor are they expected to be frequent occurrences. The total number of subjects to be enrolled is small and we plan to make notes of our observations for each subject after each session.

Specify triggers or stopping rules that will dictate when the study will end, or when some action is required. If you specified this in Section 2g [Study Endpoints], earlier in this application enter 'See 2g'.

N/A

Indicate to whom the data and safety monitoring person, board, or committee will disseminate the outcome of the review(s), e.g., to the IRB, the study sponsor, the investigator, or other officials, as appropriate.

If any AE or UAP occurs, we will follow the established timeframes for reporting to the IRB and the VA R&D Committee; i.e., immediately for any SAE or serious UAP and at annual renewal for any non-serious or expected occurrence.

Select One:

- Y The Protocol Director will be the only monitoring entity for this study.
This protocol will utilize a board, committee, or safety monitor as identified in question #2 above.

10. Benefits

- a) **Describe the potential benefit(s) to be gained by the participants or by the acquisition of important knowledge which may benefit future participants, etc.**

It is possible that individuals who participate in the FES-Rowing group will increase (or reduce loss of) bone mass in their legs and/or experience other health/fitness benefits. In addition, findings from this study may contribute to the development of knowledge which may eventually benefit individuals with spinal cord injury.

Subjects in both groups will be provided with the results of their DXA hip scans which they will be encouraged to share with their personal physician. A knowledge of bone density at the hip can be considered a minor benefit experienced by participants.

11. Privacy and Confidentiality

Privacy Protections

- a) **Describe how the conditions under which interactions will occur are adequate to protect the privacy interests of participants (e.g., privacy of physical setting for interviews or data collection, protections for follow-up interactions such as telephone, email and mail communications).**

Initial identification of potential participants will be done by a patient's personal physician who is familiar with our planned study. Follow-up interactions with potential participants will be by telephone for answering any additional questions a potential participant might have, or in person in a private, laboratory setting, for any subject who prefers to meet in person.

Confidentiality Protections

Title : Skeletal Health in the Lower Limbs Following Spinal Cord Injury
Approval Period: 01/13/2015 - 09/02/2015

- b) Specify PHI (Protected Health Information). PHI is health information linked to HIPAA identifiers (see above). List BOTH health information AND HIPAA identifiers. If you are using STARR, use the Data Privacy Attestation to ensure that your request will match your IRB-approved protocol. Be consistent with information entered in section 15a.**

Name, date of birth, telephone number and address will be obtained from each participant. We will also obtain information on injury history, including date of injury for each participant. We may also acquire photographs or video of participants while performing any research-related tasks. This information will be stored on a secure VA server. We will also use the VA Form 10-3203 ("CONSENT FOR USE OF PICTURE AND/OR VOICE") as required by VA (attached).

- c) You are required to comply with University Policy that states that ALL electronic devices: computers (laptops and desktops; OFFICE or HOME); smart phones; tablets; external hard disks, USB drives, etc. that may hold identifiable participant data will be password protected, backed up, and encrypted. See <http://med.stanford.edu/datasecurity/> for more information on the Data Security Policy and links to encrypt your devices.**

Provide any additional information on ALL data security measures you are taking. You must use secure databases such as RedCap <https://med.stanford.edu/researchit/infrastructure/redcap.html>. If you are unsure of the security of the system, check with your Department IT representative. Please see <http://med.stanford.edu/irt/security/> for more information on IRT Information Security Services and http://www.stanford.edu/group/security/securecomputing/mobile_devices.html for more information for securing mobile computing devices. Additionally, any PHI data on paper must be secured in a locked environment.

By checking this box, You affirm the aforementioned. Y

Any data on paper will be kept in a locked filing cabinet in [name] locked office or in a locked filing cabinet in a locked room designated for the storage of human subjects documents, such as signed informed consent forms. These rooms are located in a secure VA building accessible only by VA badge access. De-identified, electronic information will be stored on a secure VA server. Data analysis will only occur on de-identified data and will occur on password-protected computers.

- d) Describe how data or specimens will be labeled (e.g. name, medical record number, study number, linked coding system) or de-identified. If you are de-identifying data or specimens, who will be responsible for the de-identification? If x-rays or other digital images are used, explain how and by whom the images will be de-identified.**

Each subject will be given a code number and data for each subject will be identified by code number only. The electronic file that links the code number with a subject's name will be kept on a secure VA server. [name] will be responsible for de-identification and coding of all data files.

- e) Indicate who will have access to the data or specimens (e.g., research team, sponsors, consultants) and describe levels of access control (e.g., restricted access for certain persons or groups, access to linked data or specimens).**

Only members of the research team will have access to the data.

- f) If data or specimens will be coded, describe the method in which they will be coded so that study participants' identities cannot be readily ascertained from the code.**

Data for each subject will be given a unique code number that is unrelated in any way to a subject's III or PHI.

- g) If data or specimens will be coded, indicate who will maintain the key to the code and describe how it will be protected against unauthorized access.**

Title : Skeletal Health in the Lower Limbs Following Spinal Cord Injury
Approval Period: 01/13/2015 - 09/02/2015

[name] will maintain the key to the code. The key to the code will be kept on a secure VA server.

- h) If you will be sharing data with others, describe how data will be transferred (e.g., courier, mail) or transmitted (e.g., file transfer software, file sharing, email). If transmitted via electronic networks, describe how you will secure the data while in transit. See <http://www.stanford.edu/group/security/securecomputing/> <http://www.stanford.edu/group/security/securecomputing/>. Additionally, if you will be using or sharing PHI see <https://uit.stanford.edu/security/hipaa> <https://uit.stanford.edu/security/hipaa>.**

Data will not be shared outside of the investigator group.

- i) How will you educate research staff to ensure they take appropriate measures to protect the privacy of participants and the confidentiality of data or specimens collected (e.g. conscious of oral and written communications, conducting insurance billing, and maintaining paper and electronic data)?**

All members of the research team will complete all trainings required by VA Research Administration, including all human subjects related trainings. In his weekly meeting with study staff, [name] will discuss and reinforce the importance of privacy.

12. Potential Conflict of Interest

Investigators are required to disclose any financial interests that reasonably appear to be related to this protocol.

Financial Interest Tasks

Investigators	Role	Email	Has Financial Interest?	Date Financial Interest Answered	Date OPACS Disclosure Submitted	Date OPACS Review Completed
[name]	PD	[contact]	N	07/15/2014	N/A	N/A
[name]	OC	[contact]	N	07/15/2014	N/A	N/A

13. Consent Background

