The objective of this study is to determine if participation in an FES-rowing exercise program can better preserve bone density in the lower limbs of individuals with spinal cord injury than have others types of activities or rehabilitation strategies. Previous literature studies using animals and computer models suggest that the repetitive mechanical stimulation derived from regular participation in a FES-rowing program may be sufficient to attenuate bone loss following SCI. No further animal studies or computer models can confirm the actual benefit in humans, therefore there is no other way to obtain this information without using human subjects.

2. Study Procedures

a) Please SUMMARIZE the research procedures, screening through closeout, which the human subject will undergo. Refer to sections in the protocol attached in section 16, BUT do not copy the clinical protocol. Be clear on what is to be done for research and what is part of standard of care.

In this study we expect to enroll a total of 10 participants with SCI. Five participants will be assigned to a Standard-of-Care (control) group and five participants will be assigned to an FES-rowing intervention group. Group assignment will be partly based on the preference of each potential participant and their willingness to make the necessary time commitment required for participation in a given group, with the added goal, to the extent possible, of matching the two groups for age, gender and time since injury. Only those individuals who have a strong desire to participate in a regular exercise program and who express a willingness to travel to VA Palo Alto the necessary number of times per week to perform FES-rowing will be potential candidates for inclusion in the rowing group.

Bone density measurements for both the Standard-of-Care group and the FES-rowing group will be performed using Dual energy X-ray Absorptiometry (DXA) and peripheral Quantitative Computed Tomography (pQCT). The Standard-of-Care group will undergo no other research procedures.

Title : Skeletal Health in the Lower Limbs Following Spinal Cord Injury
Approval Period: 01/13/2015 - 09/02/2015

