The identification of potential participants from VA Palo Alto will be facilitated by [name], who is an Attending Physician in the Spinal Cord Injury Service at VA Palo Alto, and by [name], who is the Director of Clinical Research in the VA Palo Alto Spinal Cord Injury Center. In the course of performing their standard clinical responsibilities, both [name] and [name] are in regular contact with inpatients and outpatients in the VA SCI Center. Clinical colleagues of Drs. [name] and [name] whom we will tell about our planned study, will also assist in identifying potential subjects during the course of their standard clinical interactions with patients. A similar situation exists for [name] who is the Chief of Spinal Cord Injury at the Santa Clara Valley Medical Center in San Jose. Any patients who appear to be possible candidates for the study will be told briefly about the study by Drs. [name] and [name], or by their clinical colleagues, and if a patient expresses an interest in the study, they will be given contact information for [name]. Interested patients will be able to ask any additional questions by contacting [name].

- h) Inclusion and Exclusion Criteria.
Identify inclusion criteria.**

Subjects in the rowing groups:
· male and female SCI outpatients or inpatients
· have a T1 to T12, ASIA-A or ASIA-B, spinal cord injury
· be at least 18 year old

Title : Skeletal Health in the Lower Limbs Following Spinal Cord Injury
Approval Period: 01/13/2015 - 09/02/2015

- have their physician's clearance to exercise
- between 3 and 12 months post spinal cord injury
- minimum passive hip flexion range of motion (ROM) from 20 to 100 deg
- minimum passive knee flexion ROM from 20 to 100 deg
- minimum passive ankle ROM from +10 deg (dorsi-flexion) to -15 deg (plantar-flexion)
- currently use a manual wheelchair
- be able to perform independent and safe transfers to and from their wheelchair

Subjects in the control group:

- male and female SCI outpatients or inpatients
- have a C5 to T12, ASIA-A or ASIA-B, spinal cord injury
- be at least 18 year old
- between 3 and 12 months post spinal cord injury
- be able to perform safe transfers to and from their wheelchair, either independently or with assistance

Identify exclusion criteria.

Exclusion Criteria

- pregnant women
- women of childbearing potential not practicing a reliable method of contraception
- women who are post-menopausal
- have mechanical instability of the spine

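### Minor design point: controls may have a C5–C8 injury or need assisted transfers while rowers may not, and the matching covers neither trait

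*Combined protocol and SAP*

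**What the plan says.** Section 8(h) gives separate inclusion lists for the two groups.

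- **Injury level.** Rowers must "have a T1 to T12, ASIA-A or ASIA-B, spinal cord injury"; controls must "have a C5 to T12, ASIA-A or ASIA-B, spinal cord injury".
- **Transfers.** Rowers must "be able to perform independent and safe transfers to and from their wheelchair"; controls must "be able to perform safe transfers to and from their wheelchair, either independently or with assistance".
- **Rower-only items.** These include "currently use a manual wheelchair" and "minimum passive knee flexion ROM from 20 to 100 deg", with similar hip and ankle items and a physician's clearance to exercise.

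The ASIA grades, the minimum age, the window of 3 to 12 months since injury and the exclusion list, which covers bone-active medication, are common to both groups.

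On allocation, section 2(a) says: "Group assignment will be partly based on the preference of each potential participant and their willingness to make the necessary time commitment required". It adds the aim, as far as feasible, of "matching the two groups for age, gender and time since injury". Both groups have DXA and pQCT at 0, 8, 22 and 36 weeks (section 4(c)).

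Section 2(g) sets the goal as preliminary data on five rowers, summarised descriptively. Sections 1(b) and 1(c) compare rowing with earlier reports and other rehabilitation approaches.

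**The concern.** The control group is the only concurrent comparison in the study, and bone scans are the only research procedure its members undergo. The plan seeks comparable groups by matching, yet the matching factors omit two traits on which its own criteria allow the groups to differ. A person with a C5–C8 injury, or who needs help to transfer, can enter only as a control. A person eligible for both groups who is keen to exercise may well choose to row, and so leaves the pool that would supply the most comparable controls.

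If some controls are of that kind, a difference in bone change between the groups reflects rowing together with case mix. A reader could not tell the two apart without knowing each participant's injury level and transfer ability.

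**Working it through.** **The plan's own figure.** The only figure to reproduce is enrolment: 5 controls + 5 rowers = 10, which agrees with the stated total. It is a recruitment target. No power, precision, error rate or between-group test is attached to it.

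**Criteria set against matching.**

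| Trait | Rowers, 8(h) | Controls, 8(h) | Matching factor, 2(a) |
|---|---|---|---|
| Injury level | T1–T12 | C5–T12 | No |
| Transfers | Independent only | Independent or assisted | No |
| ASIA grade | A or B | A or B | Not needed |
| Time since injury | 3–12 months | 3–12 months | Yes |
| Minimum age | 18 | 18 | Age: yes |

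On both differing traits the rowers' range lies inside the controls' range. Overlap is therefore possible but not assured: every control could meet both rowing criteria, or some could fall outside them. The sections on procedures, endpoint and eligibility contain nothing that steers control selection toward the overlap.

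**Size.** The documents say nothing about how leg bone loss varies with injury level or transfer ability, so no bias can be calculated. The following is an illustration on assumed values only. Let *k* of the 5 controls be C5–C8 or need assistance. Let *D* be the difference between their mean bone change and that of the other controls, in between-participant SDs. Then

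shift in (rowing − control) = −(*k*/5) × *D*.

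- *k* = 1, *D* from −1 to +1: −(1/5) × *D* runs from +0.2 to −0.2 SD.
- *k* = 3, *D* from −1 to +1: −(3/5) × *D* runs from +0.6 to −0.6 SD.
- *D* = 0: no shift, whatever *k* is.

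**Chance of at least one such control**, if a share *p* of available controls is of this kind (*p* assumed; the candidate mix is not given): 1 − (1 − *p*)^5, which is 41% for *p* = 10%, 76% for *p* = 25% and 97% for *p* = 50%.

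**Precision for comparison.** With five per group and equal SDs, the 95% half-width for the difference in means is t(0.975, 8 df) × √(2/5) = 2.306 × 0.632 = 1.46 SD. Sampling error would exceed the illustrative shifts above.

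**The case against.** The strongest reply is that the point concerns a contrast the plan never defines. The stated goal is descriptive data on five rowers, and the benchmark is earlier reports. Nothing in the documents ties injury level or transfer ability to bone. The groups share ASIA grade, the time window and an exclusion list that removes bone-active drugs. With 1.46 SD of sampling uncertainty, one atypical control hardly matters. The rower-only items on clearance and range of motion are plainly conditions for doing the exercise. People who could row but cannot give the time may become controls, so some overlap will arise anyway. Finally, section 2(a) is a summary for the ethics board, and the VA Proposal listed in section 16 may say more.

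Most of this stands, and it limits the point to a minor one. The reply does not remove the asymmetry. Matching and identical scan schedules show that some comparison is intended, and imprecision does not cancel confounding.

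A reader might go further and infer that the rowing-control comparison is biased, that rowing will look better than it is, or that the study's main conclusion is compromised. The documents support none of these. They give no direction, they allow full overlap, and the main comparison they describe is with earlier reports. Nor does a count of differing criteria, or of controls who might fall outside the rowers' range, measure bias.

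**Conclusion.** The point holds as a minor design matter. The eligibility criteria allow the groups to differ by design in injury level and transfer ability, and the matching goal addresses neither. Any rowing-control contrast could be mixed with case mix of unknown size and direction, possibly zero. No stated number, sample size or analysis is in error.

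This rests on three things: the criteria and matching text as written; the inference, from matching and parallel scans, that some descriptive contrast will be shown; and the absence of contrary detail in the VA Proposal, which could not be checked.

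**What to change.** Leave section 8(h) and the three matching factors unchanged.

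**Section 2(a)**, after the matching sentence, add:

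> Among control candidates who have declined or cannot commit to rowing, and who are otherwise equally well matched on age, gender and time since injury, those with a T1–T12 injury who transfer independently will be enrolled first. Other eligible controls will still be accepted.

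This yields to both the rowing quota and the existing matching, so it does not compete for rowers.

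**Section 2(g)**, add:

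> Injury level and transfer ability will be listed for each participant. If any control has a C5–C8 injury or needs assisted transfers, the descriptive rowing-control contrast will also be shown using only controls with a T1–T12 injury who transfer independently, as individual values if fewer than two remain. Any difference will be described as an association.

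The individual-values rule is needed because one control gives no SD and none gives no contrast.

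**Cost.** The change is wording only. Both traits must already be known to apply 8(h), and section 11(b) already collects injury history. The downsides are a somewhat narrower first-choice control pool, whose size cannot be stated because the candidate mix is not given, and a supplementary contrast resting on five or fewer controls.
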